### **Baseline**

Data will be collected on psychosocial factors (social support, quality of marital relationship, empowerment and functional disability, behavioral activation). We will also collect data on other socio-demographic variables including maternal age (years), maternal weight (kg), socio-economic assets (adapted from the Pakistan DHS), (44) marital status (married, single, widowed), education (years of formal education completed), and literacy (literate, semi-literate, not literate) and medically-related variables including gestational age of current pregnancy, number of pregnancies, history of SGA, LBW, PTB, stillbirth, and any complications in previous pregnancies/births. We will also collect data on current medications and current medical status, i.e. gestational diabetes, hypertension, anemia, mid-upper-arm circumference, smoking, substance abuse, and medication use for depression (though we expect these last three to be uncommon). An intimate partner violence (IPV) screening question will be administered so that referrals can be made if any women experience IPV. Women in the biological sub-study will also have their blood drawn (up to 20 mL) by a study clinician or a research assistant trained in phlebotomy. Each participant will be scheduled as close to possible to the same time of day during the morning hours for all four blood draws (as blood is drawn in HFH between 8:00am and 1:00 pm), allowing us to control for diurnal variation in cytokine levels. Blood will be collected in sodium-heparin tubes for immune cell preparation. Blood will be centrifuged within 8 hours of collection by low-density gradient centrifugation via a Z326 High Performance Centrifuge. Plasma will immediately be frozen in cryovials at -80 C in a ThermoScientific Revco RLE Ultra-Low Lab Freezer and will be stored there until it is shipped to Baltimore for analysis at the end of the trial.

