Pregnancy conditions: medical status in pregnancy (e.g. pre-eclampsia, gestational diabetes)	X			X	X	X
Adverse event review					AT ALL TIMES	

\*Baseline assessment may be the same day or up to two weeks after screening.

Note: Full descriptions of the assessment tools are given in section 8.2.3.

\*\*Assessments will be somewhat flexible; the 6-week postpartum visit can be done a week early and up to three weeks after the 6 week mark (if scheduling issues preclude collecting data exactly at the desired time)

§This screener will be administered in order to be able to refer women with IPV to counseling, since it is considered an adverse event.

§§Anthropometry will be measured either our team or a healthcare provider at the 6 week postpartum visit.

[figure not shown]
2. Describe the number and type of study visits and/or contacts between the study team and the participant, how long they will last, and where/how they will take place.

For the assessments there will be a screening visit at the time of enrollment, visit at baseline (either at the same time if the woman is ready to enrol or within 2 weeks afterwards if she would like more time to think about it), in late pregnancy, at delivery, and at 6 weeks postpartum. See above for assessments that will be done at each visit. We expect baseline and the 6 week postpartum visits to last between 1 to 1.5 hours. We expect the 3rd trimester visit to be shorter, around 45 minutes. We expect the birth visit to only entail 5 minutes of data collection with the women, while the rest will be gathered from medical records.

For women randomized to the intervention, there will be 6 core intervention sessions and up to 2-6 booster sessions (depending on the time of enrolment). The first five core sessions will be delivered weekly as early in the pregnancy as possible, then the booster sessions will occur, with one final core session (Core Session 6) in the 3rd trimester. Booster sessions will be scheduled on a case by case basis, depending on the recruitment time of the pregnant mother. Please see Table 2 above for an outline of session content.

For women in the biological substudy, there will be an additional visit at 24 weeks gestation for a blood draw and HADS administration. See the Figure below for a timeline of study visits.

Figure: Timeline for participants in the intervention and control arms of the main trial

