**Plan to minimize risk (B):** We recognize IPV is an issue that is associated with both anxiety and depression. It has high prevalence rates in urban Pakistan (47). All women will be assessed on a IPV screener at the baseline and 3rd trimester visits as well as the 2013 DHS IPV instrument at the six-week postpartum visit. This will allow us to identify any women needing referrals because of IPV. All women participating in the study regardless of study arm will receive information about where they can seek care for IPV (i.e. the Institute of Psychiatry.) This program, like our prior Thinking Healthy Program (THP) that used CBT to reduce depression, includes several components – related to family engagement, education, problem solving, facilitating women to tap into their support networks– that will help address potential IPV. We have also identified potential interventions based on the WHO's Problem Management+ (PM+) (48, 49) for IPV, which are being reviewed in detail before the start of the trial. Women who report IPV will be referred to the Institute of Psychiatry, Rawalpindi Medical College, where they can receive social services and support for IPV.

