## COVID-19 Exposure Contingency Plans

Research team members who are found to be COVID-19 positive or experience unprotected exposure to COVID-19 will be referred to care, sent home or to the appropriate facility for required treatment, and instructed to self-isolate. These team members will not have subsequent interaction with study participants before resolution of their infection, with all research study visits or other in-person activities being transferred to other staff or rescheduled to avoid exposure of participant or other staff. The staff members' equipment and workplace will be sanitized.

COVID-19 positive or exposed research study participants will be referred for appropriate testing and/or treatment and will be interviewed by phone or in person to determine possible contacts among other study participants or study staff and facilitate contact tracing. These participants will not engage in any in-person study activities until resolution of their infection. Study staff who interacted with these participants without appropriate PPE will not carry out further in-person duties until they are tested and/or complete 14 days of isolation.

- Describe the research burden for participants, including time, inconvenience, out of pocket costs, etc.

Participants may feel tired or upset by talking about stressors or concerns that make them anxious. We will allow them to take breaks if they feel the interview is long or that they would like to take a break. We will also offer them counseling, if they indicate the need for it or if we consider that they could benefit from it. We will reimburse women for transportation costs to interviews and intervention group sessions.

- Describe how participant privacy will be protected during data collection if sensitive questions are included in interviews.

All interviews and sessions will be conducted, to the extent possible, in privacy. The assessment team and non-specialist providers will be trained to explain to family members (accompanying the participant) why it is important for the interview/session to be carried out privately, unless the participant requests for family member/s to be present.

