**D. Reporting Unanticipated Problems/Adverse Events (AEs) to the IRB (all studies must complete this section):**

Describe your plan for reporting to the IRB and (if applicable) to the sponsor. Include your plan for government-mandated reporting of abuse or illegal activity.

- AEs detected by the assessment team will be collected systematically on smart phones/tablets (electronic data collection) during all outcome assessments. These will be uploaded daily to the database and the data manager will complete a daily report (detailing the participant's Trial ID, type of AE and date of the event) and forward this to the [name] (Co-I).
- AEs detected by the non-specialist providers will be first reported to [name] (one of the site PIs) who will complete the AE report on smart phones/tablets. These will be uploaded to the database and the data manager will complete the report (detailing the Trial ID, type and date of the event) and forward it to the study coordinator.
- The data manager will forward the AEs to the nominated independent psychiatrist, [name], MBBS (Department of Obstetrics and Gynecology at HFH) who is not associated with the research study or to an independent physician. [name] will do a home visit or have a telephone call with the respective participant or family member in the case of death to inquire about the details of the event and to suggest mitigation strategies (as outlined above). This assessment will be documented in a detailed narrative report regarding the nature of the AE, its relationship to the intervention, actions taken since then and actions recommended.
- The data manager will mask the participant's identity (by eliminating any identifiable information) and send these detailed narrative reports to [name] (one of the site PIs) who will in turn forward this information to the PI.
- The site PIs will forward this report to the local IRB as well as document it in periodic updates for JHU.

NOTE: The IRB does not require PROMPT reporting of all AEs, only those that are unanticipated, pose risk of harm to participants or others, and are related to the study. Anticipated AEs may be reported with the Progress Report.

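### Intimate partner violence is classed as an adverse event, and the adverse-event procedure prescribes a home visit or telephone call with no exception or safe-contact provision for it; whether violence already present at baseline enters the record is unresolved

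*Combined protocol and SAP*

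**What the plan says.** The relevant statements in the combined protocol and SAP are spread over several sections.

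- **Classification.** A footnote to Table 4 (Section V, Follow-up) states: "This screener will be administered in order to be able to refer women with IPV to counseling, since it is considered an adverse event". It sets no limit by visit or by onset. The adverse-event review row of the same table covers every time point.
- **When IPV is asked.** Section VII, in the plan for the IPV risk, says: "All women will be assessed on a IPV screener at the baseline" and third-trimester visits, with the DHS IPV instrument at six weeks postpartum. The Baseline subsection gives the purpose: "An intimate partner violence (IPV) screening question will be administered so that referrals can be made if any women experience IPV".
- **Reporting.** Section X.D states: "AEs detected by the assessment team will be collected systematically on smart phones/tablets (electronic data collection) during all outcome assessments". It continues: "The data manager will forward the AEs to the nominated independent psychiatrist", or to an independent physician. That clinician "will do a home visit or have a telephone call with the respective participant or family member in the case of death", asks about the event, suggests mitigation, and writes a narrative that covers its relationship to the intervention.
- **Privacy.** Section VII states: "All interviews and sessions will be conducted, to the extent possible, in privacy". The staff trained to explain this to relatives are the assessment team and the non-specialist providers.
- **Referral.** The outside-care item of Section V and the IPV plan in Section VII refer women who report IPV to the Institute of Psychiatry.
- **Frequency.** On IPV, Section VII says: "It has high prevalence rates in urban Pakistan". No rate is given.

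**The concern.** The protocol treats talking about IPV as a risk of the study and takes care over where the question is asked. The adverse-event procedure then prescribes a second contact about the same disclosure, by visit or telephone, made by someone outside the named privacy training, and says nothing about how that contact is kept safe. The partner, who is the subject of the disclosure, may be in the home or within hearing of a call. The safety procedure could therefore create the kind of harm that the rest of the protocol tries to avoid.

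There is also a recording question. The screener is given at baseline. If violence reported there is logged as an adverse event, the record will mix pre-existing circumstances with events that arise during the trial, and the narrative will have to judge the relationship to the intervention of something that came before it.

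**Working it through.** The documents give no figure that bears on this point, so the check is a comparison of texts.

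**Does an IPV disclosure lead to a visit or call?**

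1. The Table 4 footnote makes IPV an adverse event without restriction.
2. Every woman is asked about IPV at baseline, in the third trimester and at six weeks.
3. Section X.D forwards the adverse events with no filter by type, seriousness or relatedness.
4. The step that follows is a visit or a call. No third option, such as a private conversation at the hospital, is given.
5. Section X.D does not mention IPV, although its template prompt asks for the plan on mandated reporting of abuse.
6. The referral passages in Sections V and VII do not say that referral takes the place of the contact in Section X.D.

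Steps 1 to 6 together mean that following the text leads to a visit or a call.

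**Is the contact protected?** Section V (number and type of visits) places all assessments in the hospital. Section I allows some longer interviews by telephone under the COVID-19 precautions, so disclosure in hospital is the rule rather than a certainty. The privacy statement in Section VII concerns interviews and sessions. Nothing extends it, or the associated training, to the independent clinician.

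**Does IPV present at baseline count?** The texts point in different directions.

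| Place | What it implies for IPV at baseline |
|---|---|
| Table 4, footnote and adverse-event row | Included: no limit by visit or onset, review at every time point |
| Section V, removal of participants | Doubtful: adverse events are new clinically relevant findings, and the preceding sentence concerns findings after enrollment |
| Section X.D, read with the design overview in Section III.A | Probably excluded: assessors collect adverse events at outcome assessments, and outcome data are described as collected at birth and six weeks postpartum |

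No passage says which of these governs.

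**The case against.** Much can fairly be said on the other side.

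- **Not necessarily at home, and not through relatives.** A reader might infer that every woman who discloses will be questioned at home. The text allows a telephone call instead and does not say where she takes it. The contact is with the woman herself; a family member is approached only if she has died. What stands is that she may be visited or telephoned, with no safeguard stated.
- **Silence rather than contradiction.** Section X.D does not say that the contact is not private, and its reference to mitigation outlined above may point back to the IPV referral. This is fair, but an intention to replace the contact is not written down.
- **Baseline IPV is not expressly an adverse event.** This is correct. It follows from the footnote read literally, and two other passages weigh against it. The defect is that the matter is unresolved.
- **Counts by arm are not spoiled.** A reader might infer that baseline IPV would make adverse-event counts by arm uninterpretable. Section X.D records the type and date of each event, randomization should roughly balance prior IPV, and the documents describe no formal comparison of adverse events by arm. Any effect would be mainly dilution, and it can be separated out if the record is flagged.
- **Deterrence of later answers is conjecture.** A woman contacted in this way might answer differently afterwards. IPV is a secondary outcome and its six-week report is a moderator, but nothing in the documents shows such an effect. The moderator analysis is declared exploratory, and the primary endpoint does not depend on IPV answers.

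**Conclusion.** The point holds as a gap in the safety procedure. IPV is declared an adverse event, adverse events lead to a visit or a call, and nothing exempts IPV or provides for safe contact. It should be corrected because the risk to participants is avoidable and the change is small. The status of IPV already present at baseline is a separate inconsistency between Table 4, the section on removing participants and Section X.D.

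The size cannot be stated. It is tempting to apply an assumed rate to the 1200 women: 10% would give 1200 × 0.10 = 120 and 40% would give 1200 × 0.40 = 480 contacts from the baseline visit alone. The documents do not support such a figure. The rate is an assumption, and the calculation also takes baseline IPV to be inside the adverse-event pathway; if it is outside, the number from that visit is zero.

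The conclusion rests on Section X.D being applied as written. If site procedures outside these documents already provide for safe contact, the correction is only to write that down.

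**What to change.** **Section X.D.** Except IPV from the default visit-or-call step. State that study contact about an IPV disclosure is made only in private at the hospital, or by a means the woman agreed to when she disclosed it. The second option is needed because six weeks postpartum is the last assessment, so a disclosure made there has no later study visit at which to follow it up.

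**Table 4 footnote, Section V (removal of participants) and Section X.D.** Reconcile the three. Record IPV reported at the baseline visit as a baseline characteristic, flagged separately from IPV reported at later visits, so that any adverse-event summary by arm can leave it out. The flag should follow the visit of report rather than a judgement of new or worsened violence. A single screening question at two visits, followed by a different instrument at six weeks, cannot support that judgement. The flag will not show that violence first reported later also began later.

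Referral to the Institute of Psychiatry under Sections V and VII is unchanged. These changes concern only how the study makes its own contact and keeps its own record.

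**Cost.** A few sentences and one field on the form. Some narratives may be completed later or with less detail.

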**E. Other IRBs/Ethics Review Boards:**

If other IRBs will review the research, provide the name and contact information for each IRB/ethics review board and its Federal Wide Assurance, if it has one (available on OHRP's website at <http://www.hhs.gov/ohrp/assurances>).

Federal Wide Assurance No: FWA 00010167, Human Development Research Foundation (HDRF), Islamabad, Pakistan

**F. Collaborations with non-JHSPH Institutions:**

For studies that involve collaboration with non-JHSPH institutions, complete the chart below by describing the collaboration and the roles and responsibilities of each partner, including the JHSPH investigator. This information helps us determine what IRB oversight is required for each party. Complete the chart for all multi-collaborator studies.

**Insert Name of Institutions in Partner column(s); add additional columns if necessary.**

	JHSPH	Partner 1 Human Development Research Foundation	Partner 2 University of Liverpool
Primary Grant Recipient	X		
Collaborator		X	
Collaborator			X

**For the following, indicate "P" for "Primary", "S" for "Secondary" (as appropriate to role and level of responsibility.) Add additional items if useful.**

1.	Human subjects research ethics training for data collectors	S	P	
2.	Day to day management and supervision of data collection		P	
3.	Reporting unanticipated problems to the JHSPH IRB/Sponsor	P		
4.	Hiring/supervising people obtaining informed consent and/or collecting data		P	
5.	Execution of plan for data security/protection of participant data confidentiality, as described in the Data Security and Confidentiality Protections section above	S	P	
6.	Biospecimen processing, storage, management, access, and/or making decisions about future use	--	--	--

**COMPLETE THE FOLLOWING SECTIONS WHEN RELEVANT TO YOUR STUDY:**

## **XI. Secondary Data Analysis of Existing Data:**

### **A. Study Design:**

1. Describe your study design and methods. The study design must relate to your stated aims/objectives.
  
2. Provide an estimated sample size and an explanation for that number.
  
1. Provide a brief data analysis plan and a description of variables to be derived.

### **B. Participants:**

1. Describe the subjects who provided the original data and the population from which they were drawn.
  
2. If you are receiving, accessing, or using data from a U.S. health care provider, the need for HIPAA review is likely. If you plan to bring identifiable health information from a foreign country to a U.S. covered entity (e.g., lab at the Hopkins SOM), HIPAA may be triggered. If either of these conditions is met, check "yes" to the HIPAA question in the PHIRST application.
  
1. If you plan to analyze human specimens or genetic/genomic data, provide details about the source of those specimens and whether they were collected using an informed consent document. If yes, explain whether your proposed use is "consistent with" the scope of the original consent, if it potentially introduces new analyses beyond the scope of the original consent, and/or if it introduces new sensitive topics (HIV/STDs, mental health, addiction) or cultural/community issues that may be controversial.

## **XII. Oversight Plan for Student-Initiated Studies:**

1. For student-initiated studies, explain how the PI will monitor the student's adherence to the IRB-approved research plan, such as communication frequency and form, training, reporting requirements, and anticipated time frame for the research. Describe who will have direct oversight of the student for international studies if the PI will not personally be located at the study site, and their qualifications.
  
2. What is the data custody plan for student-initiated research? (Note: *Students may not take identifiable information with them when they leave the institution.*)

**XIII. Creation of a Biospecimen Repository:**

Explain the source of the biospecimens, if not described above, what kinds of specimens will be retained over time. Clarify whether the specimens will be obtained specifically for repository purposes, or will be obtained as part of the core study and then retained in a repository.

- a. Describe where the biospecimens will be stored and who will be responsible for them.
- b. Describe how long the biospecimens will be stored, and what will happen at the end of that period.
- c. Explain whether the biospecimens will be shared with other investigators, inside and outside of JHU, how the decision to share will be made, and by whom. Include your plans, if any, for commercial use. Also explain how downstream use of the specimen will be managed, and what will happen to left-over specimens.
- d. Describe whether future research using the biospecimens will include specimen derivation and processing (cell lines, DNA/RNA, etc.), genomic analyses, or any other work which could increase risk to participants. Explain what additional protections will be provided to participants.
- e. If future research could yield unanticipated incidental findings (e.g., an unexpected finding with potential health importance that is not one of the aims of the study) for a participant, do you intend to disclose those findings to the study participant? Please explain your position.
- f. Explain whether the specimens will be identifiable, and if so, how they will be coded, who will have access to the code, and whether the biospecimens will be shared in linked (identifiable) form.
- g. Explain whether the repository will have Certificate of Confidentiality protections.
- h. Explain whether a participant will be able to withdraw consent to use a biospecimen, and how the repository will handle a consent withdrawal request.
- i. Describe data and/or specimen use agreements that will be required of users. Provide a copy of any usage agreement that you plan to execute with investigators who obtain biospecimens from you.

